2. SYNOPSIS

Name of Sponsor: National Highway Transportation Safety Administration (hereafter referred to as NHTSA)
Name of Study Drug: Cannabis
Name of Active Ingredient: Bulk cannabis (6.18% THC/ <0.025% CBD) in a 500mg dose providing 30.9 mg THC
Title of Study: Validation of the Drug Impaired Driving Scenario (DIDS) On the CRCDS-Mini-Sim: Evaluating Sensitivity To The Effects of Cannabis and Alprazolam Protocol
Number of Sites and Study Location: This study will take place at 1 site in the US. NADS, University of Iowa, Iowa City, IA.
Phase of Development: 1
Planned Duration of Participation: Approximately 42 days, including up to 14 days for Screening, 2 days in each of 3 treatment periods, each separated by at least a 7-day washout period, and a follow-up phone call approximately 7 days after discharge from the final dosing period
Objectives: Primary: The primary objective of this study is to validate the Drug Impaired Driving Scenario (DIDS) using the CRCDS-2 driving simulator, by assessing the acute effects of cannabis relative to placebo on simulated driving performance. Assay sensitivity will be demonstrated by the significant effect of alprazolam 0.75 mg on driving and cognitive endpoints. Other: 
• A secondary objective to assess the effects of cannabis on cognitive and psychomotor functioning relative to placebo• Another objective is to evaluate the potential relationship between cannabis blood concentration and driving performance endpoints
Endpoints: Key Endpoint: 
• Standard Deviation of Lateral Position (SDLP) Other Key Endpoints: 
• Driving Performance Endpoints
○ Lane exceedance; including number, maximum duration, and area of exceedance○ Excessive speed count○ Average speed and speed deviation○ Excessive A_y (cornering speed threshold exceeded) and Total Crashes○ Divided Attention: Correct Responses, Omission Errors, Commission Errors, Reaction Time, Standard Deviation of Reaction Time○ Traffic light violations

- Gap decision making performance
 - Response to Crash Likely Events
 - Attention to mirrors task
 - Working memory task
 - Coherence
- CogScreen Symbol Digit Coding Test
 - Number of correct responses
 - Response Accuracy
 - Standard deviation of reaction time
- CogScreen Symbol Digit Coding – Immediate Recall
 - Immediate recall accuracy
- CogScreen Symbol Digit Coding – Delayed Recall

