Experimental research investigating the effects of cannabis on driving have been conducted with over-the-road and simulated driving tests. There has been little consistency in the methodology applied across researchers and generally a lack of replication. Investigators have studied drivers with markedly different characteristics which likely interact with the effect of the drug (e.g., patterns of substance use, prior driving experience, and age). Published studies also show a wide range of doses and delivery systems and generally fail to show an association between exposure and serum THC. Furthermore, driving simulator studies have not been conducted using anything approaching a standard set of driving challenges or tasks.

In spite of these methodological issues, there is general agreement that cannabis increases weaving. However, the relationship between cannabis exposure and magnitude of weaving remains to be determined. The impact of cannabis on lane crossings has been inconsistent. Cannabis (without concomitant alcohol consumption) generally results in slower driving speeds and greater headway distances in nighttime conditions. With respect to neurocognitive testing, cannabis has consistently been shown to impact performance under multitasking conditions.

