PURPOSE OF PRESENT STUDY: The primary purpose of the current study is to establish a standardized protocol for assessing drug impaired driving. Validation of this methodology is to be accomplished with a study using cannabis, alprazolam, and matching placebo. As part of this research effort, investigators have worked to identify the driving tasks and cognitive abilities found to be most vulnerable to the impairing effects of cannabis. In addition, an effort was made to identify the subject characteristics associated with increased vulnerability to the impairing effects of cannabis. Worked was conducted to develop a methodology for determining when drivers are safe to resume driving after drug exposure. The current study is designed to test these hypotheses.

Simulated driving will be performed using an updated version of Cognitive Research Corporation's Driving Simulator (CRCDS2 MiniSim). The prior version of this simulator has been used in dozens of driving studies submitted for regulatory review. Driving performance will be assessed using an approximate 1-hour Drug Impaired Driving Scenario (DIDS), comprised of suburban, urban and highway driving tasks. The scenarios include challenges designed to assess lane position control, speed control, safety awareness and responsivity, driving-related decision making, multitasking, and vigilance. These domains correspond to the Essential Driving Ability

Domains described by Kay and Logan (2011). In addition, cognitive functions associated with driving performance and self-report measures will also be administered.

Consistent with the principles outlined in the FDA Guidance for Industry (2017), this study includes both a positive (active) and placebo control condition. The study is designed to assess the duration of drug effects. Readiness to resume driving will be assessed using both self-report and objective testing. Subjects will include regular (daily) users and weekly users of cannabis. The intent is to assess the impact of pattern of drug use on driving performance. A cross-over study design will be utilized to maximize statistical power.

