6. STUDY OBJECTIVES AND ENDPOINTS

6.1. Study Objective

The primary objective of this study is to validate the DIDS scenarios using the CRCDS-2 driving simulator, by assessing the acute effects of cannabis relative to placebo on simulated driving performance. Assay sensitivity will be demonstrated by the significant effect of alprazolam 0.75 mg on driving and cognitive endpoints. A secondary objective of the study is to assess the effects of cannabis on cognitive and psychomotor functioning relative to placebo. Another objective of this study is to evaluate the potential relationship between THC blood concentration and driving performance endpoints.

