13.5. Pharmacodynamic Analyses

All PD analyses will use the FAS Set.

The FAS will be used for the primary analysis. Summary statistics will be provided (mean, standard deviation, median, minimum, maximum) for each treatment. Figures will be provided for the within-subject difference scores by treatment and day as both a histogram and scatter plot. Data listings for driving simulator data will be provided.

SDLP data will be analyzed using a mixed model for repeated measures (MMRM) with fixed effects for sequence, period, and treatment and random effect for subject. A log-transformation of SDLP values to obtain normal distribution of data will be considered, if necessary. An unstructured covariance structure and Kenward-Roger degrees of freedom will be used. In the event an unstructured covariance structure fails to converge, a variance components covariance structure will be assumed. In addition to treatment effect, p-values for significance testing of period and sequence effects will be provided. Pair-wise comparisons of differences in means and two-sided 95% CIs on differences will be provided for all active treatments versus the placebo treatment.

The comparison of primary interest is cannabis versus placebo on Day 2 as a function of frequency of self-reported cannabis use. The statistical significance of alprazolam versus placebo ($p < 0.05$) comparison for SDLP is considered only to validate the experiment and having the ability to detect effects (i.e., assay sensitivity).

Formal statistical tests (when performed) will be 2-sided and tested at the $\alpha=0.05$ level of significance. Cannabis will be considered non-inferior to placebo if the two-sided upper 95% confidence limit on the difference in SDLP between that dose and placebo is less than 4.4 cm, and it can be concluded that the effect of cannabis on driving is less than that seen at 0.05% BAC, which is a level associated with increased crash risk. No adjustment to alpha levels will be made for either the comparison of alprazolam to placebo, or for secondary endpoints or analyses.

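### Section 13.5 names no cannabis result that validates DIDS, and its favourable cannabis conclusions do not depend on the alprazolam check, so an insensitive scenario could be read as a good result for cannabis

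*Combined protocol and SAP*

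**What the plan says.** **Purpose.** The study title describes a validation of DIDS by "Evaluating Sensitivity To The Effects of Cannabis and Alprazolam". Section 6.1 sets the primary objective: to "validate the DIDS scenarios using the CRCDS-2 driving simulator, by assessing the acute effects of cannabis relative to placebo on simulated driving performance". Section 5.1 says "Validation of this methodology is to be accomplished with a study using cannabis, alprazolam, and matching placebo", and reports from the literature that "there is general agreement that cannabis increases weaving".

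**Rule for cannabis.** Section 13.5 gives the form of the rule: "Cannabis will be considered non-inferior to placebo if the two-sided upper 95% confidence limit on the difference in SDLP". The limit refers to cannabis minus placebo. The threshold and its reading are given in these words: "is less than 4.4 cm, and it can be concluded that the effect of cannabis on driving is less than that seen at 0.05% BAC".

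**Supportive analysis.** Later in 13.5, if cannabis and placebo do not differ significantly and the paired differences are symmetric about zero, the plan allows the conclusion that cannabis does not impair driving.

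**Other relevant provisions of 13.5.** Differences from placebo with two-sided 95% CIs are planned for both active treatments. "Formal statistical tests (when performed) will be 2-sided" at the 0.05 level. Alprazolam versus placebo on SDLP (p < 0.05) serves as the assay-sensitivity check. Nothing states what follows for cannabis if that check fails.

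**The concern.** In a validation study the drug with an expected effect is the probe and the scenario is what is being tested. If the probe does not register, the first explanation to consider is that the scenario cannot detect it. Section 13.5 attaches no such reading to a null cannabis result. The only conclusions it draws from the cannabis SDLP comparison are about cannabis, and both are favourable.

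Suppose the cannabis-minus-placebo interval includes 0 and lies wholly below 4.4 cm. The objective then calls for a statement that sensitivity to cannabis was not shown. Section 13.5 calls for non-inferiority and, if the symmetry condition is met, for no impairment. A small study of an unproven scenario could thus yield a formal statement that the effect of cannabis on driving is below that at 0.05% BAC, while the validation question goes unanswered.

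**Working it through.** **1. The text.** The planned cannabis results on SDLP and the conclusions attached to them are:

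| Result on SDLP | Conclusion stated in 13.5 |
|---|---|
| Cannabis significantly worse than placebo | None about DIDS |
| Upper 95% limit < 4.4 cm | Non-inferior; effect less than at 0.05% BAC |
| Not significant, symmetric differences | Cannabis does not impair driving |
| Alprazolam not different from placebo | None stated for cannabis |

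The first and last rows are the gap. It does not depend on any number.

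**2. Inputs for the illustration.** From the documents: margin 4.4 cm and two-sided 95% limits (13.5); about 12 randomized, with a target of 6 to 8 completers (Synopsis). The plan gives no power figure, effect size or SD, so there is nothing to reproduce. Assumed: an SD of within-subject SDLP differences of 3, 4 or 5 cm; true effects as registered by the scenario of 0 to 3 cm; n = 8.

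**3. Method.** Paired t-interval: d ± h, where d is the mean difference, s its estimated SD, and h = t(0.975, n−1) × s/√n. With n = 8, t = 2.365, so at s = 3, 4, 5 the half-width is 2.365 × 3/√8 = 2.51 cm, 3.34 cm and 4.18 cm. Two events were simulated:

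- Conflict: d + h < 4.4 and d − h ≤ 0.
- Sensitivity shown: d − h > 0.

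| True effect registered | Conflict (SD 3/4/5) | Sensitivity shown (SD 3/4/5) |
|---|---|---|
| 0 cm | 92/75/57% | 2.5% each, by construction |
| 1 cm | 72/53/38% | 13/9/7% |
| 2 cm | 38/29/21% | 37/23/16% |
| 3 cm | 12/12/10% | 68/45/31% |

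With crossover residual degrees of freedom (2n − 4 = 12) the conflict figures rise slightly, for example to 95/81/63% at 0 cm and 44/33/24% at 2 cm.

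**4. A scenario insensitive to both drugs.** With both true differences 0, crossover degrees of freedom and SD 3 to 8 cm, the chance of declaring cannabis non-inferior is:

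- n = 6: 88% falling to 22%
- n = 8: 97% falling to 30%
- n = 12: 99.8% falling to 44%

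Alprazolam would reach p < 0.05 in only about 5% of such trials. If the non-inferiority conclusion also required alprazolam to be significantly worse than placebo, its probability would fall to between 0.3% and 2.5% over the same settings.

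**5. A scenario insensitive to cannabis only.** Assume an alprazolam effect of 4 to 6 cm, no registered cannabis effect, and n = 8. Among trials where alprazolam is significantly worse than placebo, the conflict still arises in about 95% (SD 3), 78 to 81% (SD 4) and 56 to 61% (SD 5). Conditioning on alprazolam alone does not cover this case.

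**The case against.** The strongest reply is that the plan already has a safeguard. The alprazolam test exists to show that the experiment can detect effects, and a wholly insensitive scenario would fail it about 95% of the time. The plan also provides the cannabis-placebo difference with its interval, so a detected effect would be seen. And failing to show a difference is logically compatible with showing the effect is below 4.4 cm. All three points stand, and they rule out several stronger readings a reader might infer:

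- *That an insensitive scenario necessarily yields a favourable cannabis result.* It could. Over the settings in step 4 the chance runs from 22% to 99.8%, because an imprecise trial misses the margin.
- *That no test of a cannabis effect is planned.* It is planned; what is missing is its interpretation.
- *That the non-inferiority rule contradicts the objective and must go.* The two statements can both be true. With n = 8, SD 3 cm and a true 2 cm effect, about 11% of trials (crossover degrees of freedom) would show cannabis both significantly worse than placebo and non-inferior. Keeping a conditional 4.4 cm comparison is defensible.
- *That alprazolam cannot vouch for cannabis.* The documents do not settle this. They do name sensitivity to each drug separately in the title.

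Two further points are fair. Section 6.1 speaks of assessing cannabis effects; that they should be detected is inferred from the title and rationale. Section 13 also defers detail to a separate SAP, which may say more. Neither removes the defect: Section 13.5 already states the favourable conclusions, and states them unconditionally.

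**Conclusion.** The concern holds in this form: no cannabis result is tied to validation of DIDS, and neither the non-inferiority conclusion nor the no-impairment conclusion depends on the alprazolam check. A failed validation could therefore be reported as a finding about cannabis. This rests on the text alone.

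The size of the risk rests on assumptions. At 8 completers and an SD of 3 to 5 cm, the conflicting result has a probability of 57 to 92% if no cannabis effect registers, 38 to 72% at 1 cm, 21 to 38% at 2 cm and 10 to 12% at 3 cm. The rows with a non-zero effect reflect low power, not insensitivity; only the 0 cm row describes a scenario that does not register cannabis. The point should be dealt with before the SAP is finalized, but it does not invalidate the design.

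**What to change.** Amend Section 13.5, and carry the same wording into the SAP:

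1. State that DIDS is shown to be sensitive to cannabis on SDLP if the lower limit of the two-sided 95% CI for cannabis minus placebo is above 0, and that otherwise sensitivity to cannabis has not been shown.
2. State that the non-inferiority conclusion is not drawn unless alprazolam is significantly worse than placebo on SDLP. Where cannabis does not separate from placebo, report the 4.4 cm comparison with the caveat that the sensitivity of DIDS to cannabis is unproven.
3. Delete the no-impairment conclusion in the supportive analysis, or place it under the same conditions. Otherwise the same problem survives there.

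The criterion in item 1 uses the overall contrast on SDLP. Section 13.5 makes the comparison by frequency of cannabis use the one of primary interest, and Section 6.2.2 lists many other driving endpoints, so the sponsor should confirm that this contrast and this endpoint carry the validation claim.

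**Cost.** Wording only; the model, intervals and data do not change. The sponsor would have fewer formal favourable statements about cannabis. The criterion is also demanding at this sample size: with 8 completers and SD 3/4/5 cm it is met in about 37/23/16% of trials at a true 2 cm effect and 68/45/31% at 3 cm. Failing it must therefore be reported as sensitivity not shown, never as a demonstration that DIDS is insensitive.

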Subjects will be discharged from NADS on the afternoon of Day 2 of each period approximately 5.33 hours post-dose, provided they are medically stable for discharge in the opinion of the Investigator based on the criteria established by the medical monitor. The subject will not be able to drive themselves home and will have transportation arranged.

After a washout of at least 7 days and no more than 10 days between administration of the last dose in one period and administration of the first dose in the next period, subjects will be readmitted to NADS on Day 1 of Period 2 and receive study drug according to the assigned treatment schedule. All study assessments will remain the same as in Period 1. The same process will be repeated for Period 3.

Seven days (± 2 days) after discharge from Period 3, subjects will receive a follow-up/end-of-study phone call from the site to evaluate the presence of any AEs and collect any new concomitant medication/procedure information.

Figure 1. Study Design

The schedule of assessments is provided in [Table 1](#).

The following regimens will be assessed:

- Treatment A: cannabis (inhaled)
- Treatment B: alprazolam 0.75 mg PO
- Treatment C: placebo PO
- Subjects receive 1 tablet of alprazolam and/or matched placebo 40 minutes prior to administration of inhaled cannabis/or matching placebo on Day 2 of each treatment period.

Treatment Sequences

Sequence	1	2	3
1	A	B	C
2	B	C	A
3	C	A	B
4	A	C	B
5	B	A	C
6	C	B	A

Number of Subjects (planned): Approximately 12 subjects will be randomized and dosed to target 6 - 8 subjects completing the 3 treatments. Efforts will be made to randomize an approximately equal number of subjects by gender. Efforts will be made to randomize an approximately equal number of “low frequency” users (1-10 uses per month) and “high frequency” users (>20 uses per month).

Eligibility Criteria:

Inclusion

1. Subject understands and provides written informed consent prior to the initiation of any protocol-specific procedures.
2. Subject is able to comprehend and willing to comply with the requirements of the protocol.
3. Subject is a healthy male or female, 19 to 45 years of age, inclusive, at Screening.
4. Subject has a regular sleep pattern (usual bedtime between 21:00 and 00:00).
5. Subject has Score <10 on Epworth Sleepiness Scale at Screening.

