13.1. Data Analysis Sets

The Randomized Set is defined as all subjects who are randomized.

The Full Analysis Set (FAS) is defined as all randomized and treated subjects that have at least one primary efficacy measure (SDLP) in any treatment period.

The Safety Set (SS) is defined as all subjects administered at least one dose of any study drug.

The PK Set is defined as all subjects in the SS who have at least one collected blood sample from which a valid blood concentration can be measured.

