13.2. Handling of Missing Data

Every attempt will be made to avoid missing data. All subjects will be used in the analyses, as per the analysis populations, using all non-missing data available. No imputation process will be used to estimate missing data.

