As a supportive analysis, pair-wise, within-subject differences in SDLP greater than 4.4 cm in absolute value will be compared using McNemar test. Furthermore, these pair-wise, within subject differences in SDLP will be tested for symmetry about zero (Laska et al., 2012) using the maximally selected McNemar test. If there is no significant difference between placebo and cannabis and if the distribution of paired differences is symmetrical around zero, it can be concluded that cannabis does not impair driving.

Driving performance, cognitive, and self-report endpoints will be evaluated and presented using a mixed model for repeated measures. Lane exceedance will be log-transformed (more specifically $\ln[x+1]$) before analyses.

A data listing for the results will be provided. Summary tables will be presented in the same format as the primary output for:

- Driving Performance Endpoints
 - SDLP
 - Lane exceedance; including number, maximum and duration of exceedance
 - Speed related measures; including speed deviation, average speed, and excessive speed count
 - Driving safety measures; including excessive Ay (cornering speed threshold-exceeded), and total number of collisions
 - Divided attention measures; including correct responses, omission errors, commission errors, reaction time, and standard deviation of reaction time

- CogScreen SDC Test
 - Number of correct responses
 - Response accuracy
 - Standard deviation of reaction time
- CogScreen Symbol Digit Coding – Immediate Recall
 - Immediate recall accuracy
- CogScreen Symbol Digit Coding – Delayed Recall
 - Delayed recall accuracy
- CogScreen Visual Sequence Comparison Test
 - Response speed
 - Response accuracy
 - Standard deviation of reaction time
- CogScreen Divided Attention Test
 - Response speed
 - Number of premature responses
 - Response accuracy
 - Number of lapses
 - Multitasking scores
- CogScreen Matching To Sample Test
 - Response speed
 - Response accuracy
 - Standard deviation of reaction time
- CogScreen Pathfinder Number
 - Response speed
 - Response accuracy
 - Response coordination
- CogScreen Shifting Attention Test
 - Response speed
 - Response accuracy
 - Standard deviation of reaction time
- CogScreen Dual Task Test
 - Tracking errors
 - Number of boundary hits
 - Previous number response speed
 - Previous number response accuracy
 - Previous number standard deviation of reaction time
 - Multitasking scores

- Test of Variables of Attention (TOVA)

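### Section 13.5 lets two non-significant tests establish an absence of driving impairment, even when the plan's own 4.4 cm confidence-limit rule is not met

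*Combined protocol and SAP*

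**What the plan says.** Section 13.5 (Pharmacodynamic Analyses) contains two routes to a reassuring statement about cannabis and SDLP.

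- **Confidence-limit rule.** If the upper limit of the two-sided 95% interval for the cannabis-placebo difference is below 4.4 cm, cannabis is non-inferior and "it can be concluded that the effect of cannabis on driving is less than that seen at 0.05% BAC". The plan describes that alcohol level as one linked to higher crash risk.
- **Supportive rule.** Pair-wise "within-subject differences in SDLP greater than 4.4 cm in absolute value will be compared using McNemar test", and the differences are tested for symmetry about zero with the maximally selected McNemar test. If there is no significant difference and the "distribution of paired differences is symmetrical around zero, it can be concluded that cannabis does not impair driving".

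The second rule does not require the first to be met, and nothing says which prevails if they differ.

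Two further statements bear on the first rule. The alprazolam-placebo "comparison for SDLP is considered only to validate the experiment and having the ability to detect effects (i.e., assay sensitivity"), with no stated consequence if it fails. And "A log-transformation of SDLP values to obtain normal distribution of data will be considered, if necessary", with no margin given for the log scale.

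On numbers, the Synopsis says: "Approximately 12 subjects will be randomized and dosed to target 6 - 8 subjects completing the 3 treatments". Section 13.1 puts in the full analysis set "all randomized and treated subjects that have at least one primary efficacy measure (SDLP) in any treatment period", and Section 13.2 uses all non-missing data. Cannabis-placebo pairs could therefore number anywhere from about 6 to 12. No SD, assumed effect or power is stated.

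**The concern.** Failing to reject a hypothesis is not evidence that it is true, least of all with 6 to 8 completers. The supportive rule makes the stronger claim (no impairment, rather than less than a stated amount) on the weaker basis (no margin, no bound on uncertainty). It also rewards imprecision: the fewer or noisier the pairs, the more easily both tests are non-significant and the more readily the conclusion follows. A report for a traffic-safety agency could then say that cannabis does not impair driving on data that cannot exclude the very effect the plan ties to increased crash risk.

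**Working it through.** The plan states no power or error rate for this rule, so there is no figure to reproduce. The check has four steps.

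**1. What the McNemar test can detect.** Count pairs above +4.4 cm against pairs below -4.4 cm. With k discordant pairs all one way, the exact two-sided p is 2 x 0.5^k: 0.0625 for k = 5 and 0.031 for k = 6. With 6 pairs, significance requires all six subjects to move in the same direction by more than 4.4 cm. The plan does not say whether the exact form is meant. The uncorrected chi-square form rejects from 4 v 0 (4²/4 = 4.0, p = 0.046).

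**2. Two data sets, no assumed SD.** A paired t interval stands in for the mixed-model contrast.

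*Eight pairs: 9, 8, 7, 6, 5.5, 5, -5, -6 cm.*
- Mean 29.5/8 = 3.69; SD 5.82; SE 5.82/√8 = 2.06.
- 95% CI 3.69 ± 2.365 x 2.06 = -1.18 to 8.56, so the 4.4 cm rule is not met.
- Mean test: t = 3.69/2.06 = 1.79, p = 0.12.
- McNemar 6 v 2: exact p = 2 x 37/256 = 0.29; uncorrected (6 - 2)²/8 = 2.0, p = 0.16.
- Symmetry: maximum statistic 4²/4 = 4.0, reached by 40 of the 256 sign patterns, p = 0.16. Tied magnitudes are ordered in the way that most favours rejection.

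Six of eight subjects worsened by at least 5 cm, yet the supportive rule allows the no-impairment conclusion.

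*Six pairs: 9, 7, 5, 3, -2, -4 cm.*
- Mean 3.00, SD 5.10, 95% CI -2.35 to 8.35.
- McNemar 3 v 0: exact p = 0.25, uncorrected p = 0.083.
- Symmetry p = 16/64 = 0.25.

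The conflict is the same.

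**3. How often the conclusion is wrong.** Assumptions: normal paired differences, true mean 4.4 cm, 200,000 simulated trials per cell. The symmetry test uses its exact null distribution over the 2^n sign patterns (size 0.031 at 6 and 8 pairs, 0.043 at 12). The plan does not say which test defines no significant difference, so three readings are shown, each combined with non-rejection of symmetry. Ranges run from SD 4 to SD 6 cm.

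| Pairs | Exact McNemar | Uncorrected McNemar | Paired mean test | 4.4 cm rule |
|---|---|---|---|---|
| 6 | 58-79% | 46-66% | 40-68% | about 2.5% |
| 8 | 36-68% | 26-55% | 23-56% | about 2.5% |
| 12 | 11-43% | 8-37% | 6-34% | about 2.5% |

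The SD matters a great deal. With 8 pairs the range across readings is 6-13% at SD 3 and 72-81% at SD 8; with 12 pairs at SD 3 it is about 1% or less.

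The joint event, no impairment concluded while the upper limit is at or above 4.4 cm, was taken from a smaller run of 6,000 trials per cell. At SD 6 it occurs in 77%, 66% and 40% of trials at 6, 8 and 12 pairs (exact McNemar), or 66%, 54% and 31% (mean test).

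**4. The two secondary gaps.**
- *Assay sensitivity.* Suppose the run is insensitive: all true differences are 0, there are 8 completers, and both contrasts share the placebo period. Pooled non-inferiority is met in 76% of trials (SD 4) to 43% (SD 6). In 72% to 41% it is met while alprazolam is also non-significant.
- *Log scale.* 4.4 cm is not a fixed ratio. At an assumed placebo SDLP of 20, 30 or 40 cm it is 24.4/20 = 1.22, 34.4/30 = 1.15 or 44.4/40 = 1.11.

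**The case against.** The analysis is labelled supportive. The formal claim rests on the confidence limit, which is sound: at a true 4.4 cm it passes in about 2.5% of trials whatever the sample size. The objective is to validate the driving scenario, not to clear cannabis, and a null result might more naturally be read as a failure of the scenario. Section 13 also leaves detail to a separate SAP. All of this is true, but the label does not limit the sentence, which states a conclusion in its own right and is the strongest safety statement in the plan.

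Missing the 4.4 cm limit does not show impairment. That is correct: the conflict is between inconclusive and no impairment, not between two opposite findings. Data that are inconclusive against 4.4 cm still cannot support no impairment.

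The percentages rest on an SD that the documents do not give, and they pool the two use-frequency groups although the comparison of primary interest is by frequency of use. That also stands, so the percentages show scale only; the worked examples do not depend on them. Analysis within groups would leave fewer pairs and make the conclusion easier to reach. Finally, when the true mean is exactly 4.4 cm the upper limit is at or above 4.4 cm in 97.5% of all trials by construction. The joint rates therefore mostly restate how often the supportive rule is satisfied.

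The two secondary gaps are partly covered: the alprazolam comparison is already said to validate the experiment, and the margin is already in centimetres. Only the explicit statements are missing.

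**Conclusion.** The concern holds. As written, Section 13.5 turns two non-rejections into a conclusion of no impairment, without a margin, without meeting the plan's own confidence-limit rule and without an order of precedence. The conflict is demonstrated by the 8-pair and 6-pair examples without assuming an SD, and it persists whether no significant difference refers to McNemar (exact or uncorrected) or to the mean contrast. At a true effect of 4.4 cm and an assumed SD of 4 to 6 cm, the false conclusion arises in 40-79% of trials with 6 pairs, 23-68% with 8 and 6-43% with 12. It would be uncommon only if the SD were small, or if nearly all 12 subjects contributed pairs and the SD were at the lower end. The seriousness rests on this one sentence; the alprazolam and log-scale points are clarifications.

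**What to change.** **Needed.** Delete the sentence that draws the no-impairment conclusion. Report the McNemar and maximally selected McNemar results descriptively. Allow a reassuring statement only in the form the confidence-limit rule already uses (effect smaller than at 0.05% BAC), and only when the upper 95% limit is below 4.4 cm.

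**Advisable at the same time.**
- State that non-inferiority is interpreted only if alprazolam differs from placebo on SDLP at p < 0.05, and that the cannabis result is otherwise inconclusive.
- State that the 4.4 cm comparison is made on untransformed SDLP, with log SDLP as a sensitivity analysis.

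The cost is protocol and SAP wording, with no change to sample size, data collection or conduct. The sponsor gives up one conclusion that the data could not support. A true 4.4 cm effect would then receive a reassuring statement in about 2.5% of trials, under the same normal-difference assumption.
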